1.3 Protocol Amendment 4 Summary of Changes

This document describes the changes in reference to Protocol Amendment No. 3 dated 11 December 2014.

The primary purpose of this amendment is to add Week 2 clinical laboratory tests. Minor grammatical and editorial changes are included for clarification proposes only. Full details on changes of text are given in Appendix F including detailed rationale. The following is a summary of the changes made in the amendment:

- Clinical chemistry tests, hematology tests, urinalysis, and estimated GFR were added at Week 2 (Visit 6).
 - Justification: Clinical laboratory tests were added at Week 2 (Visit 6) to be consistent with the current Takeda standard. Week 2 blood draw will allow full characterization of possible early postdose laboratory parameter changes that are considered relevant for monitoring with use of an ARB class of drug, including serum creatinine, electrolytes, liver enzyme tests, CPK, and hemoglobin. Mild ALT and AST elevations above ULN (but not exceeding 3×ULN) were observed in 7 of 16 subjects on Day 11 of a phase 1 study of TAK-491 in healthy Chinese subjects.
- Testing of serum lipids was added at Week 2 (Visit 6) and Week 4 (Visit 7).

 Justification: Lipids were added to the list of serum chemistry tests and are now tested at the same time points as other serum chemistry tests.
- The definition of "trough" in the primary endpoint was changed from "22-24 hours after the previous dose" to "approximately 24 hours after the previous dose".
 - Justification: For consistency with the required timing for blood pressure measurements stated in Section 9.1.5 (Vital Sign Procedures).
- The maximum volume of blood drawn at any single Visit was changed from 40 mL to 15 mL, and the approximate total amount of blood drawn for the study was changed from 185 mL for all subjects to 75 mL for male subjects and 80 mL for female subjects.
 - Justification: The central laboratory only requires 15 mL of blood per Visit. Blood for all clinical laboratory tests will now be drawn at 5 Visits with the addition of Week 2 (Visit 6). An additional 5 mL of blood will be drawn on Day -14 (Visit 2) for serum pregnancy testing in female subjects only.
- A serum pregnancy test was added to Day -14 (Visit 2), and urine pregnancy tests were removed from Day -7 (Visit 3) and Week 4 (Visit 7), such that serum pregnancy tests will be performed at Screening (Visit 1), on Day -14 (Visit 2), on Day 1 (Visit 5), at Week 4 (Visit 7), and at Week 8/ET (Visit 9), and urine pregnancy tests will only be performed on Day 1 (Visit 5).

Justification: For consistency with the current Takeda standard as serum pregnancy tests are more sensitive than urine pregnancy tests.

- Treatment information for overdose of TAK-491 was updated to include the results from the TAK-491 phase 1 renal impairment study.
 - Justification: It was concluded from the TAK-491 phase 1 renal impairment study that hemodialysis does not significantly remove TAK-536 or TAK-536 M-II from the systemic circulation.
- The definition of "postmenopausal" in the Contraception and Pregnancy Avoidance Procedure section (Section 9.1.9) was updated.
 - Justification: To make the definition consistent with the current Takeda standard.
- The definition for an SAE of congenital anomaly was corrected in Section 10.1.4. Justification: To align Takeda's definition with ICH and the USFDA definitions.

Administrative and Other Changes

- The name of the responsible medical officer was updated in Section 1.1.
- The names of the signatories and/or job titles were updated in Section 1.2.
- The List of Abbreviations was updated (Section 3.3).
- "TDC" was changed to "Takeda" throughout where applicable.
- References were updated/added, including the current US prescribing information and EU Summary of Product Characteristics (SmPC).

TABLE OF CONTENTS

1.0		ADMINISTRATIVE INFORMATION	2
	1.1	l Contacts	2
	1.2		
	1.3		
2.0		STUDY SUMMARY	
3.0		STUDY REFERENCE INFORMATION	
	3.1	Study-Related Responsibilities	17
	3.2		
	3.3		
	3.4	4 Corporate Identification	19
4.0		INTRODUCTION	20
	4.1	l Background	20
	4.2	2 Summary of Nonclinical Data	21
	4.3		
	4.4	Rationale for the Proposed Study	23
5.0		STUDY OBJECTIVES AND ENDPOINTS	24
	5.1	l Objectives	24
		5.1.1 Primary Objective	24
		5.1.2 Secondary Objective	24
	5.2	2 Endpoints	24
		5.2.1 Primary Endpoint	24
		5.2.2 Secondary Endpoints	24
		5.2.3 Additional Endpoints	24
		5.2.4 Safety	25
6.0		STUDY DESIGN AND DESCRIPTION	26
	6.1	1 Study Design	26
	6.2	2 Justification for Study Design, Dose, and Endpoints	27
	6.3	Premature Termination or Suspension of Study or Investigational Site	28

2.0 STUDY SUMMARY

Name of Sponsor:	Compound:	
Takeda Development Center Asia, Pte. Ltd.	TAK-491 (azilsartan medoxomil)	
Title of Protocol: A Phase 3, Double-Blind, Randomized, Parallel-Group Study to Compare the Efficacy and Safety of TAK-491 with Valsartan in Chinese Subjects with Essential Hypertension	IND No.: Not Applicable EudraCT No.: Not Applicable	
Study Number: TAK-491_305	Phase: 3	

Study Design:

This is a phase 3, multicenter, randomized, double-blind, parallel-group study to evaluate the efficacy and safety of TAK-491 compared with valsartan over an 8 week treatment period in Chinese subjects with essential hypertension (mean, sitting clinic systolic blood pressure (SBP) \geq 150 and \leq 180 mm Hg on Day 1).

A subgroup of approximately 60 subjects/arm from selected sites will undergo 24-hour ABPM 2 times during the study.

Primary Objective:

To evaluate the antihypertensive effect of TAK-491 compared with valsartan in Chinese subjects with essential hypertension.

Secondary Objective:

To evaluate safety and tolerability of TAK-491 compared with valsartan.

Subject Population: Subjects aged 18 and older with essential hypertension

 	
Number of Subjects:	Number of Sites:
Estimated total: 600 randomized	Approximately 20-25 sites in China
200 subjects in each treatment arm	
Dose Levels:	Route of Administration:
TAK-491 40 mg QD	Oral
TAK-491 80 mg QD	
Valsartan 160 mg QD	
Duration of Treatment:	Period of Evaluation:
8 week double-blind treatment period	7 to 14 day Screening period
	14 day Single-Blind Run-in period
	8 week Double-Blind Treatment period
	14 day Follow-up period

Main Criteria for Inclusion:

- The subject is treated with antihypertensive therapy and has a post-washout mean sitting clinic SBP ≥150 and ≤180 mm Hg on Day 1; or the subject has not received antihypertensive treatment within 28 days prior to Screening and has a mean sitting clinic SBP ≥150 and ≤180 mm Hg at the Screening Visit and on Day 1.
- The subject is a man or woman aged 18 years or older.
- In the opinion of the investigator, the subject is capable of understanding and complying with protocol requirements.

- The subject or, when applicable, the subject's legally acceptable representative signs and dates a written, informed consent form and any required privacy authorization prior to the initiation of any study procedures.
- A female subject of childbearing potential who is sexually active with a nonsterilized male partner agrees to use routinely adequate contraception from signing of informed consent through 30 days after last study drug dose.
- The subject has clinical laboratory test results (clinical chemistry, hematology, and complete urinalysis) within the reference range for the testing laboratory or the investigator does not consider the results to be clinically significant.
- The subject is willing to discontinue current antihypertensive medications on Day -21 or on Day -28 if the subject is on amlodipine or chlorthalidone.

Main Criteria for Exclusion:

- The subject has a mean sitting, clinic diastolic blood pressure (DBP) greater than 110 mm Hg at Day 1(after placebo run in).
- The subject is non-compliant (less than 70% or greater than 130%) with study medication during placebo run-in period.
- The subject has secondary hypertension of any etiology (eg, renovascular disease documented as the cause of hypertension, pheochromocytoma, Cushing's syndrome).
- The subject has a history of myocardial infarction, heart failure, unstable angina, coronary artery bypass graft, percutaneous coronary intervention, hypertensive encephalopathy, cerebrovascular accident, or transient ischemic attack.
- The subject has clinically significant cardiac conduction defects (eg, third-degree atrioventricular block, sick sinus syndrome).
- The subject has hemodynamically significant left ventricular outflow obstruction due to aortic valvular disease or hypertrophic obstructive cardiomyopathy.
- The subject has severe renal dysfunction or disease (based on estimated glomerular filtration rate <30 mL/min/1.73 m²) at Screening.
- Subject has known or suspected unilateral or bilateral renal artery stenosis.
- The subject has a history of cancer that has not been in remission for at least 5 years prior to the first dose of study drug. (This criterion does not apply to those subjects with basal cell or Stage 1 squamous cell carcinoma of the skin).
- The subject has type 1 or poorly controlled type 2 diabetes mellitus (hemoglobin A1c [HbA1c] >8.5%) at Screening.
- The subject has hyperkalemia (defined as serum potassium above the normal reference range of the central laboratory) at Screening.
- The subject has an alanine aminotransferase (ALT) or aspartate aminotransferase (AST) level of greater than 2.5 times the upper limit of normal (ULN), active liver disease, or jaundice at Screening.
- The subject has any other known serious disease or condition at Screening (or Randomization) that would compromise subject safety, might affect life expectancy, or make it difficult to successfully manage and follow the subject according to the protocol.
- The subject has a history of hypersensitivity or allergies to hypersensitivity to TAK-491 (azilsartan medoxomil), any of its excipients or other angiotension II (AII) receptor blockers (ARBs).
- If female, the subject is pregnant or lactating or intending to become pregnant during the participation in this study; or intending to donate ova during such time period.

- The subject currently is participating in another investigational study or is receiving or has received any investigational compound within 30 days prior to the first dose of the study medication.
 - Note: This criterion does not apply to subjects who participated in observational studies that lacked an intervention or invasive procedure.
- The subject is an immediate family member, study site employee, or is in a dependant relationship with a study site employee who is involved in conduct of this study (eg, spouse, parent, child, sibling) or may consent under duress.
- The subject has a history of drug abuse (defined as any illicit drug use) or a history of alcohol abuse within the past 2 years.
- The subject is taking or expected to take an excluded medication listed in Section 7.3 of the protocol.
- The subject works a night (third) shift (defined as 11 PM [2300] to 7 AM [0700]). (Only for subjects with ambulatory blood pressure monitoring (ABPM).
- The subject has an upper arm circumference <24 cm or >42 cm. (Only for subjects with ABPM.)

Main Criteria for Evaluation and Analyses:

The primary endpoint is change from baseline to Week 8 in trough (approximately 24 hours after the previous dose) sitting clinic SBP.

Secondary endpoints are:

- The change from baseline to Week 8 in trough sitting clinic DBP.
- Percentage of responders at Week 8, as defined by the following:
 - a) Clinic SBP <140 mm Hg and/or reduction of ≥20 mm Hg from baseline.
 - b) Clinic DBP <90 mm Hg and/or reduction of ≥10 mm Hg from baseline.
 - c) a and b
- Percentage of subjects achieving target blood pressure at Week 8, as defined by the following:
 - a) Clinic SBP <140 mm Hg.
 - b) Clinic DBP < 90 mm Hg.
 - c) Clinic SBP <140 mm Hg and DBP <90 mm Hg.
 - d) Clinic SBP <130 mm Hg.
 - e) Clinic DBP < 80 mm Hg.
 - f) Clinic SBP <130 mm Hg and DBP <80 mm Hg.

Additional endpoints are:

Statistical Considerations:

Analysis Sets:

Safety Analysis Set: All subjects who receive at least 1 dose of double-blind study medication. Subjects will be analyzed according to the study medication they received.

Full Analysis Set (FAS): All randomized subjects who received at least 1 dose of study medication. Subjects will be analyzed according to the treatment group to which they were randomized.

Subjects who were randomized more than once will be excluded from both the safety analysis set and the FAS.

Efficacy Analysis:

Unless otherwise specified, efficacy analyses will be performed using the FAS and all statistical inference will use a 2-sided 0.05 significance level. A subject will be included in the primary analyses only when there is both a baseline value and at least 1 value during the double-blind treatment period. Missing values will be imputed using last observation carried forward (LOCF) methodology. In the LOCF analysis data set, the last post-baseline double-blind observed value will be carried forward and used for all subsequent scheduled time points where data are missing (eg, the subject has missing data or has dropped out of the study).

The primary analysis will be based on an analysis of covariance (ANCOVA) model for change in clinic SBP from baseline to week 8. The model will include treatment as a fixed effect and baseline clinic SBP as a covariate. From the framework of the ANCOVA the following will be determined: treatment LS mean, LS mean for the difference between TAK-491 and valsartan, p-value and 2-sided 95% confidence intervals for the treatment difference. For the primary analysis the overall type 1 error rate of 0.05 will be controlled using the 4 step sequential test described below.

- Step 1: A test for noninferiority of TAK-491 80 mg to valsartan 160 mg will be performed using a noninferiority margin of 1.5 mm Hg. If the upper limit of the 2-sided 95% CI of the treatment difference (TAK-491 valsartan) is not greater than 1.5 then proceed to Step 2.
- Step 2: A test for noninferiority of TAK-491 40 mg to valsartan 160 mg will be performed using a noninferiority margin of 1.5 mm Hg. If the upper limit of the 2-sided 95% CI of the treatment difference (TAK-491 valsartan) is not greater than 1.5 then proceed to Step 3.
- Step 3: A test for significant difference between TAK-491 80 mg versus valsartan 160 mg will be performed at the 5% level. If the p-value is not greater than 0.05 then proceed to Step 4.
- Step 4: A test for significant difference between TAK-491 40 mg versus valsartan 160 mg will be performed at the 5% level.

Based on historical data, the observed placebo-corrected treatment effects on change from Baseline in clinic SBP for valsartan 160 mg once daily was -8.6 mm Hg. Therefore, the noninferiority margin was set conservatively at 1.5 mm Hg, which is less than one-third of the valsartan treatment effect. Accordingly, TAK-491 will be considered noninferior to valsartan when the upper limit of the 2-sided 95% CI of the treatment difference

(TAK-491-comparator) is \leq 1.5 mm Hg. The secondary endpoint, change from baseline to Week 8 in trough sitting clinic DBP will be analyzed similar to the primary endpoint, excluding the sequential testing. Change from baseline for both SBP and DBP at other visits will be summarized similar to the primary endpoint.

Additionally, similar analyses will be performed for both SBP and DBP for selected subgroups where appropriate, eg, age, sex.

The categorical secondary efficacy endpoints, percentage of subjects responding to treatment and percentage of subjects reaching blood pressure target at Week 8 will be tabulated for each of the following definitions:

- Response criteria.
 - a) Clinic SBP <140 mm Hg and/or a reduction of ≥20 mm Hg from baseline.
 - b) Clinic DBP <90 mm Hg and/or a reduction of ≥10 mm Hg from baseline.
 - c) a and b (ie, joint criteria).
- Target blood pressure.

- a) Clinic SBP <140 mm Hg.
- b) Clinic DBP < 90 mm Hg.
- c) Clinic SBP<140 mm Hg and DBP<90 mm Hg.
- d) Clinic SBP<130 mm Hg.
- e) Clinic DBP<80 mm Hg.
- f) Clinic SBP<130 mm Hg and DBP<80 mm Hg.

A logistic model with treatment as fixed effect and baseline clinic SBP as a covariate will be used to analyze response for clinic SBP. The odds ratio and its 95% confidence will be estimated. Similarly, a logistic model with treatment as fixed and baseline clinic DBP as a covariate will be used to analyze the response for clinic DBP. The joint response for both clinic SBP and DBP will be analyzed using a logistic model with treatment as fixed effect and baseline clinic SBP as a covariate. A similar analysis and model will be used to analyze the percentage of subjects reaching target blood pressure at Week 8. The percentage of subjects responding to treatment, as well as reaching blood pressure target, will also be presented for other visits, using the above methods.

Subgroups (eg, age, sex) analyses may be performed if data permit.

Sensitivity analyses to be performed on the primary endpoint (and other endpoints where appropriate) include: multiple imputation for missing values; analyses using the per protocol set; and analyses using observed values only.

Safety Analysis:

All safety assessments, including AEs, clinical laboratory test results, vital sign measurements, and 12-lead ECG results will be presented in the data listings. Treatment-emergent AEs will be summarized by treatment group. Laboratory values, pulse rate, and 12-lead ECG results will be summarized with descriptive statistics and/or shift tables.

Sample Size Justification:

Assuming an SD of 17 mm Hg and a 10% dropout rate, a sample size of 200 subjects per treatment group (total of 600 subjects) is sufficient to achieve at least 90% power to detect a difference of 6 mm Hg between TAK-491 dose and valsartan by a 2-sample t-test on the mean change from baseline to Week 8 in mean sitting clinic SBP at 0.05 2-sided significance level. This sample size will also provide, for the above assumptions, at least 90% power for demonstrating noninferiority with a margin of 1.5 mm Hg between TAK-491 and valsartan.

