The 8 week duration is sufficient to evaluate the efficacy because in all previous studies, a plateau in blood pressure reduction was observed after 4 weeks of treatment for both TAK-491 and valsartan. The study design employs a 3 to 4 week washout period to establish a true drug-free baseline blood pressure and to determine severity of hypertension in enrolled population at randomization. A coincident 2-week, single-blind, placebo run-in period is to evaluate study drug compliance. This short-term washout/placebo treatment period is not associated with increased risk of major irreversible cardiovascular events in a hypertensive population [14,15].

Frequent visits and withdrawal criteria for elevated BP during the study as defined in Section 7.5 will further ensure the safety of the study subjects.

The primary endpoint of this study is sitting, clinic SBP, which is a well-established measure for assessing antihypertensive effect and is a better predictor of cardiovascular outcomes than DBP. Clinic SBP is an appropriate primary endpoint because it is validated as a surrogate endpoint in observational and interventional clinical studies [16-18].

ABPM parameters will also be evaluated in a subset of approximately 60 patients per arm. ABPM parameters are clinically more predictive of cardiovascular outcome than clinic BP measurements, as demonstrated by numerous studies. In particular, mean 24-hour SBP is the best predictor of cardiovascular risk, even after adjustment for risk factors including clinic BP [19-21].

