7.1 Inclusion Criteria

Subject eligibility is determined according to the following criteria:

- 1. The subject is treated with antihypertensive therapy and has a post-washout mean sitting clinic SBP ≥150 and ≤180 mm Hg on Day 1; or the subject has not received antihypertensive treatment within 28 days prior to Screening and has a mean sitting clinic SBP ≥150 and ≤180 mm Hg at the Screening Visit and on Day 1.
- 2. The subject is a man or woman aged 18 years or older.
- 3. In the opinion of the investigator, the subject is capable of understanding and complying with protocol requirements.
- 4. The subject or, when applicable, the subject's legally acceptable representative signs and dates a written, informed consent form and any required privacy authorization prior to the initiation of any study procedures.
- 5. A female subject of childbearing potential* who is sexually active with a nonsterilized* male partner agrees to use routinely adequate contraception* from signing of informed consent through 30 days after last study drug dose.

*Definitions and acceptable methods of contraception are provided in Section 9.1.9 Contraception and Pregnancy Avoidance Procedure and reporting responsibilities are defined in Section 9.1.10 Pregnancy.

- 6. The subject has clinical laboratory test results (clinical chemistry, hematology, and complete urinalysis) within the reference range for the testing laboratory or the investigator does not consider the results to be clinically significant.
- 7. The subject is willing to discontinue current antihypertensive medications on Day -21 or on Day -28 if the subject is on amlodipine or chlorthalidone.

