7.2 Exclusion Criteria

Any subject who meets any of the following criteria will not qualify for entry into the study:

- 1. The subject has a mean, sitting clinic DBP greater than 110 mm Hg at Day 1 (after placebo run in).
- 2. The subject is non-compliant (less than 70% or greater than 130%) with study medication during placebo run-in period.
- 3. The subject has secondary hypertension of any etiology (eg, renovascular disease documented as the cause of hypertension, pheochromocytoma, Cushing's syndrome).

- 4. The subject has a history of myocardial infarction, heart failure, unstable angina, coronary artery bypass graft, percutaneous coronary intervention, hypertensive encephalopathy, cerebrovascular accident, or transient ischemic attack.
- 5. The subject has clinically significant cardiac conduction defects (eg, third-degree atrioventricular block, sick sinus syndrome).
- 6. The subject has hemodynamically significant left ventricular outflow obstruction due to aortic valvular disease and hypertrophic obstructive cardiomyopathy (HOCM).
- 7. The subject has severe renal dysfunction or disease (based on estimated glomerular filtration rate [GFR] <30 mL/min/1.73 m²) at Screening.
- 8. The subject has known or suspected unilateral or bilateral renal artery stenosis.
- 9. The subject has a history of cancer that has not been in remission for at least 5 years prior to the first dose of study drug. (This criterion does not apply to those subjects with basal cell or Stage 1 squamous cell carcinoma of the skin).
- 10. The subject has type 1 or poorly controlled type 2 diabetes mellitus (hemoglobin A1c [HbA1c] >8.5%) at Screening.
- 11. The subject has hyperkalemia (defined as serum potassium above the normal reference range of the central laboratory) at Screening.
- 12. The subject has an alanine aminotransferase (ALT) or aspartate aminotransferase (AST) level of greater than 2.5 times the upper limit of normal (ULN), active liver disease, or jaundice at Screening.
- 13. The subject has any other known serious disease or condition at Screening (or Randomization) that would compromise subject safety, might affect life expectancy, or make it difficult to successfully manage and follow the subject according to the protocol.
- 14. The subject has a history of hypersensitivity or allergies to TAK-491 (azilsartan medoxomil), any of its excipients or other angiotension II (AII) receptor blockers (ARBs).

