7.3 Excluded Medications and Treatments

- Antihypertensive agents, including those used for treatment of other conditions, such as benign prostatic hyperplasia (α-blockers) or edema (diuretics). Those used at screening must be discontinued for the washout/run-in period through the completion of final in-clinic procedures at Week 8/Early Termination (Visit 9). Amlodipine and chlorthalidone should be discontinued on Day -28, while all other antihypertensive medications should be discontinued on Day -21. If necessary, medications that need to be stopped gradually may be tapered in the first week of screening, but must be discontinued completely by Day -14.
- Other agents that alter BP are excluded from the beginning of the run-in period through the remainder of the study. These include:
 - Tricyclic antidepressants.
 - Monoamine oxidase (MAO) inhibitors.
 - Central nervous system stimulants.
 - Amphetamines or their derivatives.
 - Dopamine agonists.
 - Atypical antipsychotic agents.
 - Trazodone.
 - Lithium.
 - Diet medications (except orlistat).
 - Nitrates.
 - Thiazolidinediones.
- Conditionally excluded medications as specified:
 - Phosphodiesterase type 5 (PDE5) inhibitors within 72 hours of a clinic visit.

- Chronically used (defined as more than 3 doses per week) common cold medications with pseudoephedrine or phenylephrine, or nonsteroidal anti-inflammatory drugs (NSAIDs), including aspirin >325 mg/day or cyclooxygenase-2 (COX-2) inhibitors.
- Systemic use of corticosteroids (topical or inhaled is acceptable).
- Subjects will be instructed not to take any medications, including over-the-counter products, without first consulting the investigator.

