7.5 Criteria for Discontinuation or Withdrawal of a Subject

The primary reason for discontinuation or withdrawal of the subject from the study should be recorded in the case report form (electronic) (eCRF) using the following categories. For screen failure subjects, refer to Section 9.1.12.

- 1. Pretreatment event or adverse event (AE). The subject has experienced a pretreatment event or AE that requires early termination because continued participation imposes an unacceptable risk to the subject's health or the subject is unwilling to continue because of the pretreatment event or AE.
- 2. Major protocol deviation. The discovery post randomization that the subject failed to meet protocol entry criteria or did not adhere to protocol requirements, and continued participation poses an unacceptable risk to the subject's health.
- 3. Lost to follow-up. The subject did not return to the clinic and attempts to contact the subject were unsuccessful. Attempts to contact the subject must be documented.
- 4. Voluntary withdrawal. The subject (or subject's legally acceptable representative) wishes to withdraw from the study. The reason for withdrawal, if provided, should be recorded in the (e)CRF.

Note: All attempts should be made to determine the underlying reason for the withdrawal and, where possible, the primary underlying reason should be recorded (ie, withdrawal due to an AE or lack of efficacy should not be recorded in the "voluntary withdrawal" category).

- 5. Study termination. The sponsor, IRB, IEC, or regulatory agency terminates the study.
- 6. Pregnancy. The subject is found to be pregnant.
 - Note: If the subject is found to be pregnant, the subject must be withdrawn immediately. The procedure is described in Section 9.1.10.
- 7. Lack of efficacy. The investigator has determined that the subject is not benefiting from investigational treatment; and, continued participation would pose an unacceptable risk to the subject.

Note: If the mean blood pressure exceeds 180 mm Hg systolic and/or 110 mm Hg diastolic at any time after screening or randomization, the blood pressure measurement should be repeated within 48 hours. If blood pressure remains elevated, the subject should be considered for withdrawal.

8. Other.

Note: The specific reasons should be recorded in the "specify" field of the (e)CRF.

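### Treated subjects have no numeric blood pressure ceiling at Screening, so someone already above 180 systolic or 110 diastolic on drug may start washout on investigator judgement alone

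*Protocol*

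**What the plan says.** Inclusion 1 (Protocol 2.0 and 7.1) has two branches. For treated subjects: "The subject is treated with antihypertensive therapy and has a post-washout mean sitting clinic SBP ≥150 and ≤180 mm Hg on Day 1". For the others, the condition is: "has not received antihypertensive treatment within 28 days prior to Screening and has a mean sitting clinic SBP ≥150 and ≤180 mm Hg", and this must hold both at Screening and on Day 1. Exclusion 1 (7.2) sets the diastolic limit for everyone at one time point: "The subject has a mean, sitting clinic DBP greater than 110 mm Hg at Day 1 (after placebo run in").

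Section 9.3.1 has Visit 1 vital signs taken in every subject, but uses the systolic mean for eligibility only in those without antihypertensive drugs for 28 days. Section 9.3.2 holds back washout until the applicable entry criteria have been verified, and allows the subject to be told by telephone to begin.

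On the safety of washout, Section 6.2 states: "This short-term washout/placebo treatment period is not associated with increased risk of major irreversible cardiovascular events in a hypertensive population". It adds: "Frequent visits and withdrawal criteria for elevated BP during the study as defined in Section 7.5 will further ensure the safety". The relevant note in 7.5 begins: "If the mean blood pressure exceeds 180 mm Hg systolic and/or 110 mm Hg diastolic at any time after screening or randomization". It then asks for a repeat within 48 hours and, if pressure stays high, for withdrawal to be considered.

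**The concern.** Section 6.1 places Screening ahead of washout so that eligibility can be settled before existing treatment is stopped. For the only subjects who lose treatment, that check contains no blood pressure limit. Someone above 180 systolic or 110 diastolic while taking drug is already beyond the level that would bar randomization, yet the plan as written lets that drug be stopped.

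The asymmetry is hard to justify. Untreated subjects, from whom nothing is withdrawn, face a systolic ceiling of 180 mm Hg at Screening; treated subjects do not. Other risks at Screening get explicit limits in 7.2: eGFR below 30, HbA1c above 8.5%, ALT or AST above 2.5 times the upper limit of normal, and potassium above the reference range.

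What is at stake is the safety of screened subjects during washout and run-in.

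**Working it through.** No formula in the plan is at issue. The check is a reading of every blood pressure limit by visit and by prior treatment, followed by a count of days.

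**Numeric ceilings in the entry criteria (inclusion 1, exclusion 1, Section 9.3.1)**

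| Group | Screening SBP | Screening DBP | Day 1 SBP | Day 1 DBP |
|---|---|---|---|---|
| Treated | none | none | 180 | 110 |
| Untreated for 28 days | 180 | none | 180 | 110 |

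Treated subjects have 0 of 2 limits at Screening and 2 of 2 on Day 1. Untreated subjects have 1 of 2 and 2 of 2.

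**Time from stopping drug to the first numeric eligibility limit.** SAP 7.1.3 defines study days with no Day 0, so the interval from Day -a to Day 1 is a days.

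- Stop on Day -21: 21 days.
- Stop on Day -28 (amlodipine or chlorthalidone): 28 days.
- Taper ending on Day -14: 14 days. Section 7.3 allows this: "medications that need to be stopped gradually may be tapered in the first week of screening, but must be discontinued completely by Day -14".

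**Time to the first scheduled reading, for context.** Vital signs are next due at Day -14. That is 21 - 14 = 7 days after a Day -21 stop and 28 - 14 = 14 days after a Day -28 stop. The protocol's own visit spacing is similar: 14 - 7 = 7 days in run-in and 28 - 14 = 14 days between Weeks 2 and 4. Visit spacing is therefore not the complaint.

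**Does another provision fill the gap?**

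- *Section 9.3.2* enforces applicable criteria, but none that applies to a treated subject at that point contains a pressure limit.
- *Exclusion 13* opens: "The subject has any other known serious disease or condition at Screening (or Randomization) that would compromise subject safety". It gives no pressure figure and rests on judgement, across approximately 20 to 25 sites.
- *The 7.5 note* has the right figures but is worded for readings after screening, and it leads only to considering withdrawal. Even if read to cover Visit 1, it would leave the decision to the investigator.
- *Section 6.2* speaks of hypertensive subjects in general and does not address those above 180/110 on drug. Its further safeguard is the same 7.5 note.

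These provisions agree with one another. The finding is a gap, not a contradiction.

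**The case against.** The strongest reply is that this is a deliberate and coherent choice. The design wants a drug-free baseline, so it judges treated subjects after washout, and nobody above 180 systolic or 110 diastolic on Day 1 can be randomized. The investigator has the Visit 1 reading in hand. Exclusion 13 applies at Screening and also covers subjects who would be hard to manage under the protocol. Subjects with prior infarction, heart failure, stroke, hypertensive encephalopathy, secondary hypertension or severe renal dysfunction are already excluded. Pressure is measured again at Day -14 and Day -7, when the 7.5 trigger of 180/110 operates. Section 6.2 cites literature for the safety of washout, and the documents show no excess risk in this subgroup.

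Much of that stands. Many investigators would decline to wash out such a subject, the population reaching washout is already selected, and the number affected is unknown. Whether the cited literature covers these pressures cannot be settled from the documents. But the Day 1 limits act only after drug has been stopped, and the 7.5 trigger acts after screening without requiring a stop. Neither sets a limit at the moment treatment is withdrawn.

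Two criticisms of the remedy deserve an answer. Applying it to anyone medicated within 28 days before Screening may look too wide for an on-drug concern, but that is the group Section 9.3.2 says needs washout. It also leaves untreated subjects without a diastolic limit at Screening. That is true; the remedy is confined to those whose drug is withdrawn.

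**Conclusion.** The concern holds. For treated subjects the plan sets no numeric blood pressure limit before drug is stopped, and the first such eligibility limit comes nominally 21 or 28 days after an untapered stop, or 14 days after the latest permitted end of a taper. For blood pressure, the decision at Screening rests on judgement; the other entry criteria must still be met.

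The conclusion depends only on the wording of the criteria and the nominal visit days. It says nothing about how often such subjects would present or how much harm would follow, because the documents give no basis for either. The randomized population remains protected by the Day 1 limits, and the primary analysis, type I error and power are unaffected. This is an inexpensive safety improvement worth making, not a flaw in the trial's inference.

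**What to change.** Add an exclusion criterion to 7.2 and to the Section 2.0 list: *antihypertensive medication taken within 28 days before Screening, with mean sitting clinic SBP >180 mm Hg or DBP >110 mm Hg at Visit 1, confirmed on a repeat set of 3 readings within 48 hours.*

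Add two sentences to the vital-signs item in 9.3.1: *In subjects medicated within 28 days, determine mean sitting SBP and DBP. If SBP >180 or DBP >110 mm Hg is confirmed, washout (including any taper) must not begin and the subject is a screen failure.*

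Section 9.3.2 then enforces the rule unchanged, and 9.1.12 already has a suitable screen-failure category. The 180/110 cut-off is proposed by analogy with the Day 1 and 7.5 limits; the documents give no separate on-drug threshold, and the sponsor could choose a lower one.

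The cost is one criterion, two sentences, and a repeat set of readings (possibly a short return visit) for subjects above the limit. A few candidates who might have met the limits on Day 1 would be lost.
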